We will assess potential mediators of perceived risk and self-efficacy, key constructs of the Health Belief Model, ²⁶ as well as readiness for weight loss as an indicator of motivation. Perceived risk for developing diabetes will be assessed with the Risk Perception Survey for Developing Diabetes, a 53-item Likert scale measure with four subscale scores on Comparative Disease Risk, Environmental Risk, Personal Control, and Optimistic Bias. ^{41,42} Self-efficacy for weight control will be measured with the Weight Efficacy Lifestyle Questionnaire, a 20-item measure of confidence (on a 10-point scale) managing five situational factors related to weight management behavior: negative emotions, availability, social pressure, physical discomfort, and positive activities. ⁴³ We will use validated Spanish-language versions of both measures. ^{42,44} Weight loss readiness will be assessed with the Stages of Change in Overweight and Obese People (S-Weight), a 5-item survey developed concurrently in English and Spanish by expert consensus. ^{45,46} Mediators will be measured during an initial assessment at the time of enrollment and 1-2 weeks prior to the first NDPP session (i.e., about one week after pre-sessions are completed for the Pre-NDPP arm, and shortly before NDPP classes begin for both arms). This will determine whether Pre-NDPP results in increased perceived risk, self-efficacy, and readiness compared to the usual care NDPP, and whether changes in these variables mediate outcomes.

Data collection for Aim 3. RE-AIM is a planning and evaluation framework for implementation research that will guide our evaluation of Pre-NDPP delivery and effectiveness.⁸ RE-AIM constructs will be assessed through a combination of recruitment data, intervention outcomes, staff logs, observations, and interviews with Lifestyle Coaches, clinic personnel, and patients, as well as cost records (Table 1). [name] holds expertise in implementation research and will lead qualitative data collection with [name] (Qualitative Research Assistant; QRA), first developing semi-structured interview guides⁴⁷, surveys, and a structured observation template. Health economist [name] will lead cost-related data collection.

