| Risk perception | Risk Perception Survey for Developing Diabetes ⁴² | Administered by Lifestyle Coaches during first study visit | BL and 1-2 weeks prior | | | |
| Self-efficacy | Weight Efficacy Lifestyle Questionnaire ⁴³ | and repeated prior to start of NDPP classes to assess pre- | to start of NDPP | | | |
| Readiness | Stages of Change in Overweight and Obese People ^{45,46} | post change | classes | | | |
| | Implementation factors | | | | | |
| Reach – Absolute number, proportion, and representativeness of individuals who participate | # and characteristics of patients referred, outreached, and express interest, consent, complete Pre-NDPP (intervention group), and attend NDPP (both groups); Reasons for not enrolling or dropout | Demographics and referral data from EHR; enrollment and participation data collected by coaches; reasons for participating or declining collected by QRA interviews with select participants | Ongoing collection | | | |
| Effectiveness- Intervention impact on key outcomes | Based on main outcomes listed above | | | | | |
| Adoption – Absolute number, proportion, and representativeness of settings and agents willing to initiate intervention | # and characteristics of participating DH clinics; NDPP referrals; Lifestyle Coach participation | Study documentation; EHR data | Monthly abstraction analysis | | | |
| | Factors influencing adoption | QRA interviews with Lifestyle Coaches and select clinic personnel | BL (for coaches and clinic personnel); 6 months after start of Pre-NDPP (for coaches | | | |

| | | | only) |
|---|--|---|---|
| Implementation – Fidelity to intervention protocol, including | Completion of Pre-NDPP and NDPP protocol components | Coach documentation; Presession shadowing by QRA; Fidelity checks | Ongoing collection |
| consistency of delivery (e.g., bias) and time and cost of intervention | Acceptability of Pre-NDPP components, processes and tools; any adaptations made by coaches | Interivew by QRA with Lifestyle Coaches | 6 months after start of Pre-NDPP |
| | Process, barriers, facilitators to implementing Pre-NDPP | QRA interviews with select participants, select clinic personnel and Lifestyle Coaches | 12 months after start of Pre-NDPP (for clinic personnel and coaches); 1- 2 months after last intervention session attended (for participants) |
| | Pre-NDPP cost | Lifestyle Coach time and resources survey | Quarterly after each pre-session |

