Recruitment. We will identify potential participants through referrals from healthcare providers at DH, which is known to support initial enrollment in the NDPP.²¹ Providers refer through the electronic health record (EHR) per usual practice. Since 2013 over 7,000 at-risk patients were referred by providers to the DH NDPP. If needed to meet recruitment goals, we will also identify participants from a risk registry based on EHR data, which has previously identified over 10,000 NDPP-eligible patients annually. The enrollment process after initial identification will be as follows: 1) Lifestyle Coaches pre-screen via medical record review and contact referrals by phone to verify interest, eligibility, and schedule eligible individuals for an initial screening visit (held in-person or remotely as needed), 2) consenting individuals are randomized to receive Pre-NDPP or usual care NDPP (note we will use Denver Health's e-consent process for any virtually-conducted recruitment visits), and 3) complete an initial assessment (behavioral and anthropometric assessments), 4) the Pre-NDPP group completes a pre-session 1-2 weeks before NDPP classes start, 5) both groups complete a follow up behavioral

assessment 1-2 weeks before NDPP classes start (collected in-person or remotely as needed), and 6) both groups commence yearlong NDPP classes (held in-person or remotely as needed).

We will initially enroll 500 participants, with a goal of 400 randomized participants across both groups attending ≥1 NDPP session as based on statistical power estimates (see Sample Size and Power Calculations below). From previous experience, we expect approximately 50% of referred patients to express interest in participating upon initial outreach. Then after initial assessment, we expect early attrition of approximately 20% of consenting participants. We will seek to recruit 50 individuals every 3 months, for a total of 500 participants recruited over 2.5 years (i.e., 200 participants annually). From 2013-2017, we recruited 300 NDPP participants on average each year. Thus, we expect to fully meet RCT recruitment goals. Demographic characteristics of individuals in this study are expected to approximately match characteristics of all previous NDPP participants at DH: 78.0% female, 58.2% Hispanic, 19.5% NHB, 21.0% NHW, 61.4% low-income (including a majority of low-income individuals within each racial/ethnic group), and a mean age of 48.4 (SD=12.7) years.

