Description of the National Diabetes Prevention Program (for both conditions). The yearlong NDPP promotes modest weight loss through diet and physical activity. The curriculum is published by the CDC.3 We will follow CDC guidelines for implementing the standard group-based NDPP,³⁷ including 16 weekly to biweekly sessions, followed by ≥6 monthly sessions over a total of one year. The objective of NDPP is achieving ≥5% weight loss. Attending more sessions is associated with greater weight loss, 4,22 and guidelines allow NDPP sites to offer more than the minimum 22 sessions to support this goal. We will offer 25 total NDPP sessions (16 in months 1-6; 9 in months 7-12), held at the same time, day, and location in group visit rooms available at 8 neighborhood primary care clinics. There will also be an option to attend classes virtually via phone or videoconference. In light of COVID-19, in-person group classes will be offered when allowable by public health entities and Denver Health, although a virtual attendance option will remain for participants who prefer to join remotely. Two new NDPP classes will commence quarterly over 2.5 years. To minimize potential contamination, participants in the two study arms will be enrolled in separate NDPP classes. Trained, bilingual lay health educators will lead NDPP classes as Lifestyle Coaches and provide make-up sessions as needed. They will be observed by the research coordinator and/or qualitative research assistant for fidelity and to assess for potential bias in NDPP delivery. Weight is measured at each session on a high-capacity, medicalgrade scale, or by reporting their weight from a study-provided in-home scale. As required by the NDPP curriculum, participants are encouraged to achieve a weekly goal of ≥150 minutes of moderate to vigorous intensity physical activity (beginning gradually as needed). Participants are instructed to track start and stop times and report total weekly activity minutes at the following session. The most recent CDC curriculum also

encourages a low-fat diet, but does not require monitoring of dietary adherence.^{3,32} Lifestyle Coaches conduct support calls between sessions to support engagement and health behavior change, address individual questions and concerns, and remind participants about upcoming sessions.

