Hypothesis 2.1. The Pre-NDPP intervention will increase perceived risk for developing diabetes and self-efficacy and readiness for weight management. Outcomes for these analyses will be patients' perceived risk, self-efficacy, and readiness scores over time. We will use longitudinal models to determine if trajectories differ for patients in control vs. intervention groups, shown below in mixed model notation:

 $Y_{tij} = \gamma_{000} + \gamma_{010}$ (intervention) + γ_{100} (time) + γ_{110} (intervention x time) + $u_{00j} + r_{0ij} + \epsilon_{tij}$, where γ_{000} represents the initial status for control groups; γ_{010} represents the baseline difference between intervention and control groups (should be close to 0); γ_{100} is the change in scores for groups of control patients; γ_{110} is the difference in change for control vs. intervention groups. r_{tij} is a patient random effect and U_{00j} is a group random effect, independent of r_{tij} and assumed to have a bivariate normal distribution over practices; ϵ_{tij} is residual variance. Thus, the Pre-NDPP effect can be tested as H_0 : γ_{110} =0 vs H_1 : γ_{110} \neq 0.

Hypothesis 2.2. Perceived risk, self-efficacy, and readiness will mediate relationships between Pre-NDPP treatment and outcomes. Outcomes will be weight loss and session attendance, using similar approaches as described above for Hypotheses 1.1 and 1.2. We will include baseline perceived risk, self-efficacy, and readiness as covariates and change in these constructs as primary independent variables to determine if the intervention effect is partially or fully explained by these hypothesized mediators.⁵⁸

Hypothesis 2.3. Pre-NDPP effects will differ for participants with the moderator condition (e.g., Hispanic; low-income) compared to those without the moderator (non-Hispanic; higher income). The effects of moderator analyses involve inclusion of an intervention x moderator fixed effect for models that are not longitudinal (e.g., percent weight loss, number of sessions attended). For longitudinal models (e.g., self-efficacy over time) models will include a main effect for time, arm, moderator variable, time x arm, time x moderator, arm x moderator, and time x arm x moderator interaction term. The 3-way interaction term tests for differential intervention effectiveness in subgroups identified by the moderator variable.

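### The only group effect in the Hypothesis 2.1 equation cancels from the intervention-by-time test and does not match its own description, so the test is mildly anti-conservative if mediator change clusters by group

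*Combined protocol and SAP*

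**What the plan says.** The combined protocol and SAP, section IV.F, Hypothesis 2.1, models perceived risk, self-efficacy and readiness on intervention, time and their product, with random terms u00j (group), r0ij (patient) and a residual. The tested coefficient, γ110, "is the difference in change for control vs. intervention groups". The explanatory text says that the patient term "is a patient random effect and U_{00j} is a group random effect", and that the group effect is "assumed to have a bivariate normal distribution over practices".

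Section IV.A (Data collection for Aims 1 and 2) gives two mediator assessments: one at enrolment, and one "about one week after pre-sessions are completed for the Pre-NDPP arm, and shortly before NDPP classes begin for both arms". Table 1 has the mediator surveys "Administered by Lifestyle Coaches during first study visit" and repeated before classes start.

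On group structure, section IV.C says "We will seek to recruit 50 individuals every 3 months" and "Two new NDPP classes will commence quarterly over 2.5 years", with the two arms in separate classes. It also says "we expect early attrition of approximately 20% of consenting participants". The description of the Pre-NDPP protocol has coaches deliver one class of each arm every quarter. General quantitative approaches (IV.F) promises mixed models for patients within groups and for repeated measurements, but names no group term for change.

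**The concern.** The pre-session is delivered to a group between the two measurements. Any effect of a particular session, its coach or its members therefore acts on change, and γ110 is a contrast of change. Each group lies wholly in one arm, so between-group variation in change is part of the error of that contrast. The written equation has no term for it. Its one group term describes groups that are higher or lower by the same amount at both times, which does not touch change.

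The description does not settle the matter. A bivariate distribution needs two group-level terms, and the equation shows one. The two readings test γ110 against different error terms. At stake is whether the standard errors for the effects on the mediators, the first link in the Aim 2 mechanism, are too small. If the structure is chosen after the data are seen, the result is also open to selection.

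**Working it through.** **Inputs**

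- Two-sided α of .05 (General quantitative approaches).
- Two time points (IV.A).
- 10 groups of 18–20 per arm (Table 2). This agrees with IV.C: 2.5 years is 10 quarters; 50 recruits over two classes is 25 each; less 20% attrition, 25 × 0.8 = 20.
- ICC of mediator change: not given. Assumed 1–2%, the Table 2 values for weight change (pilot 1.44%).

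**The plan's own figure.** Table 2 concerns weight loss only. For 10 groups of 20 at ICC 2%, the effective size is 200 / (1 + 19 × 0.02) = 200 / 1.38 = 144.9, against 145 stated, with power about 80%. The other rows also reproduce, to within one in effective sample size. No figure is given for Hypothesis 2.1.

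**Cancellation.** Subtract the two equations for one patient:

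change = γ100 + γ110 × arm + (ε2 − ε1)

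Both u00j and r0ij are gone. With residual variance 0.4 (illustrative) and 200 per arm, the model's variance for γ110 is 2 × 0.4 × 2 / 200 = 0.008, SE 0.08944. A generalised least squares check, with u00j variance set to 0, 0.02, 0.1 and 0.5, gives 0.08944 each time with complete data. With 20% of follow-up missing it gives 0.0985–0.0986.

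**Size if only Pre-NDPP change clusters.** With m per group and ICC ρ of change, the true variance exceeds the model's by D = (1 + [1 + (m − 1)ρ]) / 2. The actual type I error is 2(1 − Φ(1.96/√D)).

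| m | ρ | D | √D | Type I error |
|---|---|---|---|---|
| 18–20 | 0 | 1 | 1 | 5.0% |
| 18 | 1% | 1.085 | 1.042 | 6.0% |
| 18 | 2% | 1.170 | 1.082 | 7.0% |
| 20 | 1% | 1.095 | 1.046 | 6.1% |
| 20 | 1.44% | 1.137 | 1.066 | 6.6% |
| 20 | 2% | 1.190 | 1.091 | 7.2% |

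The true SE is thus 4–9% larger than the model's. A simulation of change scores (40,000 trials per case) gave 6.0–7.3%.

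**Sensitivity**

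- If two coaches each deliver one class per arm every quarter, there are 20 groups of 10–12.5 per arm: 5.5–6.3%.
- If only 16 of 20 attend the pre-session (assumption), (m − 1) becomes 0.8 × 15 = 12: 5.7–6.4%.
- 1–2% is not an upper bound. At an assumed 5% with m = 20, D = 1.475 and the error is 10.7%.

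**Effects shared across arms.** The same simulation was run with m = 18–20 and a 1–2% effect on change common to the two classes of a quarter. The unpaired and paired tests compare group mean changes.

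| Clustering of change | Written test | Unpaired group-level test | Paired group-level test |
|---|---|---|---|
| Fully shared | 4.8–4.9% | 2.4–3.5% | 5.0–5.1% |
| Shared plus Pre-NDPP only | 5.8–7.1% | 2.7–3.6% | 4.9–5.2% |

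A shared effect cancels from the contrast and adds no inflation, but it makes an unpaired group-level test conservative.

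**The case against.** Several points on the other side have weight.

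- **The size is assumed.** Nothing in the documents gives an ICC for mediator change, and the borrowed figure comes from weight change in a yearlong programme. One session of 60–90 minutes, with the research coordinator assisting every time and fidelity checks, may cluster change less. This stands; at zero clustering nothing is wrong with the test.
- **The general text may cover it.** General quantitative approaches lets diagnostics inform other model specifications. That permits a group term for change but does not commit to one, while the specific equation leaves it out.
- **The analysis is minor.** Sample size and power calls mediation and moderation exploratory, and no decision depends on Hypothesis 2.1. This limits the weight of the point. But Hypothesis 2.1 tests the effect on the mediators, with its own stated null.

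Three stronger readings are tempting, and the documents do not support them.

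- A reader might infer that usual-care change clusters too, since coaches administer the surveys. Then D = 1 + (m − 1)ρ, and the error would be 7.0% (m = 18, 1%) to 9.5% (m = 20, 2%). That formula needs usual-care groups to vary independently of Pre-NDPP groups. Coaches take one class of each arm per quarter, so coach or quarter effects common to both arms cancel.
- A reader might take the bivariate wording as proof that a group slope was intended. The same sentence speaks of practices rather than groups and labels the patient effect rtij where the equation has r0ij. Leftover text is as likely.
- A reader might carry the problem over to the weight outcome. Hypothesis 1.1 has a single outcome per patient, and its group effect sits in the intercept that carries the treatment effect.

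**Conclusion.** The point holds, at modest size. Equation and description in Hypothesis 2.1 conflict whatever one assumes about clustering, and the plan does not say which model will be fitted. In the linear model, the group intercept as written gives the γ110 test essentially no protection against clustering of change.

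The consequence is conditional. It needs the equation fitted as shown and some clustering of change within Pre-NDPP groups. At an assumed ICC of 1–2% with 10 groups of 18–20 per arm, 5% becomes about 6.0–7.2%. The cancellation was not checked for an ordinal or other non-linear link, which the plan allows and which readiness might need. The correction should be made before analysis, but it does not threaten the trial's main conclusion.

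**What to change.** - State the group structure to be fitted, and make the equation, the distributional description and the labels (group or practice, r0ij or rtij) agree.
- Add a group-by-time random effect, and test γ110 with Satterthwaite or Kenward–Roger degrees of freedom.
- Because classes of the two arms are matched by coach and quarter, also include a pair-by-time effect, or analyse group mean changes in pairs. Otherwise a shared effect makes the test conservative.
- Arm-specific group variances are optional.
- Name a fallback for fits that return no usable degrees of freedom. In trial fits with arm-specific variances, 2–6% did so.
- If readiness is modelled with another link, include the corresponding group term for change.

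The cost is one or two random terms in the SAS code and a wording correction, with no new data. Intervals for γ110 widen. With 10 groups per arm, the group-by-time term leaves about 18 degrees of freedom (critical value 2.101 against 1.966). In simulation, intervals were about 5% wider on average at ICC 0 and 10–15% wider at ICC 1–2% in the Pre-NDPP arm. Full pairing leaves 10 − 1 = 9 degrees of freedom (critical value 2.262) and costs more: about 12% at ICC 0 and 17–22% at ICC 1–2%. If a shared effect is the only source of clustering, pairing is the cheaper choice, at about 11% against 14–24% unpaired.

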Hypothesis 1.1. Pre-NDPP participants will experience greater weight loss than those directly enrolled into NDPP. The primary outcome for this analysis will be percent weight change among all randomized participants. As study participation includes groups of individuals in the same study arm, the data structure will be hierarchical, with patients nested within groups. Statistical models are shown in hierarchical notation below.

Likelihood of achieving ≥5% weight loss in the NDPP will also be evaluated (using generalized linear mixed models with logit link), as well as percent weight change from first to last NDPP sessions attended.

Level 1 model. Individual outcomes will be modeled as a function of patient characteristics (fixed effects), such as sociodemographic variables, baseline BMI, and comorbid conditions: $Y_{ij} = \beta_{0j} + \beta_{1j} X_{1ij} + \beta_{2j} X_{2ij} + ... + \beta_{pj} X_{pij}$ Level 2 model. Group level models specify relationships between group-level predictors and coefficients in the Level 1 model. The intervention effect is included as 0 if control, 1 if intervention: $\beta_{0j} = \gamma_{00} + \gamma_{01}$ (intervention)+ u_{0j} . Thus, for a standardized model, γ_{00} is adjusted mean weight loss for patients in the standard condition (i.e., no pre-session intervention), γ_{01} represents the average increment (decrement) from the mean for groups with intervention patients, and u_{0j} is a group level random effect that reflects between-group variance and is the difference between group means and the predicted mean based on the model, and $u_{0j} \sim N(0,\tau_{00})$. Thus, Hypothesis 1.1 can be tested as H_0 : γ_{01} =0 vs H_1 : γ_{01} ≠0.

Hypothesis 1.2. Pre-NDPP participants will have greater engagement in the NDPP than those who are directly enrolled into the program. The outcome variables, number of sessions attended and days of participation, will be analyzed using similar approaches. If the distribution of outcomes is non-normal we will use generalized linear mixed models with the appropriate distribution and link function, as described above. We will also examine the dichotomous outcome of ≥1 NDPP session attended using multilevel logistic regression (generalized linear mixed model with logit link and random effect for group).

Aim 2: To examine mediators and moderators of Pre-NDPP outcomes.

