Sample size and power. Pre-NDPP pilot data indicate a 0.36 effect size for percent weight change in the NDPP with an intraclass correlation coefficient (ICC) of 1.44%. To be conservative for our primary outcome of percent weight loss among all randomized participants regardless of NDPP participation, we estimate minimum effect sizes detectable for various sample sizes and ICCs (Table 2), with effect sizes of approximately 0.28 to 0.35 for analyses of the primary outcome with a type-1 error rate of .05. Consequently, we expect that 500 randomized participants will provide adequate power while accounting for expected attrition. Note that mediation and moderation analyses are considered exploratory, as estimated power is unknown.

| Table 2: Estimated power to detect treatment differences in percent weight loss. | | | | | |
|--|-----------------------|-----|-----------------------|---|-------|
| Groups per arm | Patients per group | ICC | Effective sample size | Detectable difference (effect size) | Power |
| 10 | 18 (180 per arm) | 1% | 154 | .32 | 80% |
| 10 | 18 (180 per arm) | 2% | 134 | .35 | 82% |

| 10 | 20 (200 per arm) | 1% | 168 | .31 | 81% |
|----|------------------|----|-----|-----|-----|
| 10 | 20 (200 per arm) | 2% | 145 | .33 | 80% |
| 12 | 20 (240 per arm) | 1% | 201 | .28 | 80% |
| 12 | 20 (240 per arm) | 2% | 174 | .31 | 82% |

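### Hypothesis 2.2 judges mediation by whether the arm effect is explained away, with no pre-specified test or interval for the indirect effect

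*Combined protocol and SAP*

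**What the plan says.** Section IV.F, Hypothesis 2.2, enters the baseline scores of the three constructs as covariates and "change in these constructs as primary independent variables". The stated purpose is "to determine if the intervention effect is partially or fully explained by these hypothesized mediators". A methods reference is cited, but the text gives no null hypothesis, no interval and no definition of partial or full.

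The outcomes are described only in general terms: "Outcomes will be weight loss and session attendance, using similar approaches as described above for Hypotheses 1.1 and 1.2". Hypothesis 1.1 concerns percent weight change, but adds: "Likelihood of achieving ≥5% weight loss in the NDPP will also be evaluated (using generalized linear mixed models with logit link". Hypothesis 1.2 concerns number of sessions and days of participation, and adds: "We will also examine the dichotomous outcome of ≥1 NDPP session attended using multilevel logistic regression".

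Two other statements bear on the point. Hypothesis 2.1 formally tests the effect of arm on change in each construct ("Thus, the Pre-NDPP effect can be tested as" a zero arm-by-time coefficient). The sample size section says: "Note that mediation and moderation analyses are considered exploratory, as estimated power is unknown".

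**The concern.** Hypotheses 1.1 and 2.1 each state a null hypothesis, and 2.3 names the interaction term to be tested. Hypothesis 2.2 asks instead for a judgement on how far the arm effect shrinks. Without an interval or a criterion, the reader has two readings to hand: the arm effect stopped being significant (full), or it became smaller (partial). Both can happen by chance. On the logit scale the coefficient also moves for a reason unrelated to mediation.

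Section II says that uptake should be greater if providers and payers can understand how Pre-NDPP works, and assigns that question partly to the mediation analysis. A verdict of full mediation that rests on a p-value crossing 0.05 would serve them poorly, as would real mediation that went unseen.

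**Working it through.** **The plan's own figures.** The only power figures are in Table 2, for percent weight loss. Effective sample size per arm is g·m / (1 + (m − 1)·ICC). For 10 groups of 20 with ICC 1% this is 200 / 1.19 = 168.1 (stated 168). Power at 0.31 SD is Φ(0.31·√(168.1/2) − 1.96) = 81.1% (stated 81%). The other five rows also reproduce. None of them concerns mediation.

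**Assumed inputs.** The documents give no path values. Let a be the arm effect on mediator change and b the effect of mediator change on outcome, both in SD units; c is the total effect and c′ the direct effect. I assume a and b of 0.2 to 0.3 and 168 to 200 per arm, treated as effective numbers. Total effects are 0.29 to 0.36 SD: Table 2 has detectable effects of 0.28 to 0.35, and 0.36 is the pilot effect.

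**Step 1: is the point quantity sound?** With a linear model, the same patients and the same covariates, c − c′ = a·b. In simulated trials the two agreed to about 1e-15. For percent weight change the drop in the arm coefficient is therefore the right quantity; its uncertainty is what is missing.

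**Step 2: how often is significance lost when mediation is only partial?** With outcome SD 1:

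- SE(c) = √(2/n)
- SE(c′) = √(2/n)·√(1 − b²)·√(1 + a²/4)
- Power = Φ(effect/SE − 1.96)

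The last column is the fall in power from c to c′, divided by the power for c.

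| n per arm | c | a = b | a·b | c′ | Power, c | Power, c′ | Lost, given c significant |
|---|---|---|---|---|---|---|---|
| 168 | 0.33 | 0.3 | 0.09 | 0.24 | 85.6% | 62.6% | 27% |
| 200 | 0.29 | 0.2 | 0.04 | 0.25 | 82.6% | 71.9% | 13% |
| 168 | 0.36 | 0.2 | 0.04 | 0.32 | 91.0% | 84.6% | 7% |
| 168 | 0.36 | 0.3 | 0.09 | 0.27 | 91.0% | 72.8% | 20% |

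Simulation agrees. In the first row 22.6% of all trials lose significance and 85.4% have a significant total effect: 22.6 / 85.4 = 26.5%. In the second row repeated simulations gave 12 to 14%. The true mediated share is 0.09/0.33 = 27% in the first row and 0.04/0.29 = 14% in the second, so mediation is far from full in both.

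**Step 3: what would an interval add?** Simulation with 168 per arm:

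- No mediation (a = 0, b = 0.3, c = 0.33): a significant arm effect shrinks by 10% or more in 11.8% of trials. A Monte Carlo interval for a·b excludes zero in 5.3%.
- Partial mediation (a = b = 0.3, c = 0.33): the interval excludes zero in 76%.
- No total effect (c = 0, a = b = 0.3): the total effect is significant in 5%, so there is rarely an effect to explain. The interval still detects the indirect effect in 78%.

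**Step 4: the logit scale.** Adding a predictor unrelated to arm increases the arm log odds ratio. With intercept 1.2 and conditional log odds ratio 0.50, the log odds ratio without the predictor is 0.48, 0.43 and 0.37 for predictor slopes of 0.5, 1.0 and 1.5 per SD. The increase on adding it is 4%, 17% and 36%; at slopes of 0.2 and 0.3 it is 0.6% and 1.4%. At slope 1.5 the implied attendance is about 70% and 77% in the two arms.

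As a share explained, for ≥5% loss (pilot ratio 3.5 taken as an odds ratio, assumed control rate 20%):

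| a | b (log odds per SD) | Apparent share | Product share, ab/(c′ + ab) |
|---|---|---|---|
| 0 | 0.3 / 0.5 / 1.0 | −2% / −5% / −19% | 0% |
| 0.5 | 0.3 / 0.5 / 1.0 | 10% / 15% / 21% | 12% / 19% / 34% |
| 0.2 | 1.0 | −3% | 13% |

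For ≥1 session (assumed control rate 80%, odds ratio 1.5) the apparent shares with a = 0 are −1%, −4% and −14%.

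**The case against.** Four points can be made for the plan, and much of each stands.

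1. A reader might infer that Hypothesis 2.2 goes untested. The documents do not support that. Hypothesis 2.1 formally tests arm on mediator, and the 2.2 model yields a coefficient for mediator on outcome. A joint-significance test could be assembled from the two, and in the simulations it behaves much like the product interval. The plan does not say that it will be.
2. A reader might infer that the plan judges full mediation by loss of significance. It never says so. That is one natural reading of an undefined criterion, and the cited methods reference may set another. The 12 to 27% describes what that reading would do.
3. A reader might infer that the logistic outcomes are definitely part of 2.2 and seriously distorted. They are not named there; they arrive only through the reference to similar approaches under 1.1 and 1.2. The distortion is about 1 to 5 points for weak to moderate mediators. It mostly hides mediation, so it would not by itself produce a false claim of full mediation. Slopes of 1.0 or more mean odds ratios of at least 2.7 per SD, and nothing in the documents supports a questionnaire change being that predictive.
4. The analysis is declared exploratory, Section IV.E repeats that power for mediators is limited, and the Aim 3 interviews examine mechanism separately. This lowers the stakes. It does not supply an interval, and unknown power makes one more useful.

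**Conclusion.** The gap is real but modest: an exploratory analysis with no pre-specified test, interval or criterion for the indirect effect. For percent weight change the planned comparison estimates the right quantity and lacks only its uncertainty. If loss of significance is taken as the sign of full mediation, about 12 to 27% of trials with a significant total effect would suggest it wrongly at total effects of 0.29 to 0.33 SD. At 0.36 SD the figure is about 7% with paths of 0.2 and about 20% with paths of 0.3.

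The logit problem is conditional on those outcomes entering 2.2, and is material only for strong mediators. All path values and control rates, and the unclustered effective sample sizes, are assumptions. The 0.36 SD is the pilot's figure for weight change within the NDPP, so it may be optimistic for all randomized participants. This is a worthwhile improvement, not a defect that threatens the primary analysis.

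**What to change.** In the text of Hypothesis 2.2:

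- Name the outcomes, and say whether ≥5% loss and ≥1 session are among them.
- For each mediator, and for all three jointly, estimate the indirect effect from a mediator model and an outcome model with the same baseline covariates.
- Give a 95% interval that respects class clustering: a Monte Carlo product interval from the mixed models, or a class-level bootstrap. Table 2 has only 10 to 12 classes per arm, so the bootstrap would rest on few clusters and the text should say so.
- Report any binary outcome on the risk-difference scale.
- Replace the partial-or-full verdict with the estimate and its interval, still labelled exploratory.

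No new data are needed. Section IV.A already places both mediator assessments before classes begin: "Mediators will be measured during an initial assessment at the time of enrollment and 1-2 weeks prior to the first NDPP session". The cost is some SAP wording and analysis time. The intervals will be wide, which is a fair picture of what the trial can say about mechanism.
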